9.6 Data Management

All data will be entered by sites into an eCRF that will be used to build the study database. Data abstraction will be done approximately every 6 months $(\pm 30 \text{ days})$ starting from enrolment. Additional data on neuropsychomotor development will be assessed through specific questionnaires (paper and/or electronic) which will be administered at pre-specified intervals starting at enrolment (approximately every 6 months [± 30 days] for patients up to 6 years old and approximately yearly [± 60 days] for patients from 6 years old) either in person or via telephone interview or mail. The score and percentiles from the questionnaires will be used for the final analysis. The final analysis cohort will be constructed from the complete review of inputted data documenting events in a patient's history from primary disease diagnosis until the earliest occurrence of the following events: death, withdrawal of consent, end of available data in the chart, completion of the 12-year follow-up period, or up to the age of 25 years. Data to be abstracted include variables relating to ALL diagnosis, ALL-associated treatment, development impairment, HSCT-associated AEs, leukemia relapse, long-term AEs, secondary malignancy until the earliest of: death, withdrawal of consent, end of available data in the chart, completion of the 12-year follow-up period, or 25 years of age.

Each patient will be assigned a unique identification number at the time of the first data entry. This unique identification number will be used to link data to subsequent data entries. The data will be abstracted by site staff from patient medical records into a web-based electronic data capture (EDC) system, using an electronic abstraction form that will provide an integrated, transparent tool to facilitate and record center recruitment, case identification, patient selection and study progress at the center and patient level.

The EDC system will include eCRFs designed to capture the variables and outcomes of interest. The data collected for this study will derive from medical records that are kept per routine clinical practice for the documentation and decision-making for a patient's care or study-specific questionnaires (paper and/or electronic). The sponsor will provide protocol-specific training on the eCRFs to all study site abstractors in advance of the study data collection period to ensure clarity on the questions and the data to be captured are accurate. Some fields in the eCRFs will include drop-down lists (eg, gender, dates), others will be radio buttons (eg, check all disease/conditions in the patient's medical history: diabetes, hypertension, stroke).

9.6.1 Review and Verification of Data Quality

Upon entry of the data by the study site staff, Amgen will check the data for potential errors and inconsistencies. The data will be evaluated for potential outliers, missing information, and logical consistency with the study variables. Sites will be queried for clarification if unlikely values, potential errors, or inconsistencies are identified. The investigator and study staff should verify the data against medical records, and investigator will confirm and guarantee, by signing, the accuracy and integrity of the data corresponding to the information contained in the medical records.

9.7 Data Analysis

9.7.1 Planned Analysis

Bi-annual summaries of the data will be done for inclusion in specified PSURs estimated to commence with the subsequent PSUR occurring at least 12 months after start of data collection to allow adequate time to accrue treated patients after approval and the start of the study.

9.7.2 Planned Method of Analysis

All analyses will sub-grouped by blinatumomab consolidation or chemotherapy consolidation group. Continuous variables will be summarized by mean, median, standard deviation, 25th percentile, 75th percentile, minimum and maximum. Categorical variables will be summarized by number and percentage. For categorical outcomes, 95% confidence intervals will also be presented where appropriate. For time-to-event endpoints, Kaplan-Meier (KM) curves and estimates (median, 1st and 3rd quartile) of the time-to-event endpoint with 95% confidence intervals will be calculated, if estimable. Tables will be presented for the total patient population (ie, those who meet the eligibility criteria). Pending adequate sample size is enrolled (≥50 patients per arm), comparison analysis between blinatumomab and chemotherapy groups will be conducted by logistic

or Cox regression models generating an odds ratio or hazard ratio with 95% CI confidence intervals.

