- For all patients, the Vineland Adaptive Behavior Scales-Third Edition (Vineland-3) Comprehensive Parent/Caregiver Form will be used. The Vineland-3 is a widely used and validated measure of adaptive behavior across core areas of Communication (receptive, expressive, and written language), Daily Living Skills (personal, domestic, and community), Socialization (interpersonal relationships, play and leisure, and coping skills), and Motor Skills (gross motor and fine motor) (Sparrow et al, 2016). An additional section on Maladaptive Behaviors is included that assesses for problem behaviors related to internalizing (eg. anxiety, depression) and externalizing (eg, aggression, conduct problems, psychosis) conditions. The Vineland-3 will be re-administered to patients ages 0-5 years every 6 months in order to capture the more rapid rate of typical development; parents (guardian) of patients (or other informant, for adult patients) ages 6 years and older will complete the form every year.
- Cognitive skills are indirectly captured by the Vineland-3 particularly for children under the age of 2 via its assessed domains. To supplement assessment of more advanced cognitive skills for patients ages 2+ the Behavior Rating Inventory of Executive Function (BRIEF) will also be used. This form is similarly well-validated and widely used to assess executive functions in paediatric and adult populations (Gioia, Isquith,Guy, & Kenworthy, 2015). The preschool form (BRIEF-P) is available for ages 2-5 and assesses higher-order cognitive skills in the areas of Inhibitory Self-Control, Flexibility, and Emergent Metacognition (eg, inhibit, shift, emotional control, working memory, plan/organize). The parent form (BRIEF-2) is applicable for ages 6-18 and assesses areas of Behavioral

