Regulation (inhibit, self-monitor), Emotion Regulation (shift, emotional control), and Cognitive Regulation (initiate, working memory, plan/organize, task monitor, organization of materials). For patients ages 19+, the informant report form will be completed by a parent (guardian) or other adult who knows the patient well (BRIEF-A Informant); skills are evaluated in the areas of Behavioral Regulation (inhibit, shift, emotional control, self-monitor) and Metacognition (initiate, working memory, plan/organize, task monitor, organization of materials). The BRIEF will be re-administered to patients ages 2-5 years every 6 months in order to capture the more rapid rate of typical development; parents (guardian) or informants of patients ages 6 years and older will complete the form every year.

- A complete written manual describing administration and scoring procedures will be created by study neuropsychologist who has thorough knowledge of and experience with these measures. Initial personalized training of these procedures with study personnel will also be provided, along with ongoing consultation as needed.
- Neurological impairment defined as:
 - Peripheral nervous system disorders (including neuromuscular junction)
 - Central nervous system disorders
- Endocrine impairment defined as:
 - Hypothalamus-Pituitary-Gonadal Axis disorders
 - Hypothalamus-Pituitary-Adrenal (HPA) Axis disorders
 - Hypothalamus-Pituitary-GH Axis disorders
 - Hypothalamus-Pituitary-Thyroid Axis disorders
- o Immune system impairment defined as:
 - leukopenia (neutropenia and/or lymphopenia)
 - Iow IgG
 - low IgM
 - low IgA
 - Autoimmune disorders
 - Vaccination failure

Secondary Objectives

- HSCT-related AE defined as any second malignancy; Graft versus Host Disease (GvHD); infection, and/or; relapse
 - o Acute GvHD data includes
 - Grading of disease by either National Institute of Health (NIH) or Seattle Criteria
 - Organ involvement: skin; gut; liver; lung; eye; mouth' musculoskeletal, and/or; other

- GvHD associated symptoms: thrombocytopenia (<100 G/l); eosinophilia (Absolute Eosin Count: AEC > 500x10/L); bronchiolitis obliterans; bronchiolitis obliterans organizing pneumonia (BOOP); polyserositis, and; other
- Resolution
- Chronic GvHD data includes:
 - Diagnosis based upon clinical or histological evidence
 - Diagnosis of progressive, quiescent, or de novo disease
 - Grading of disease by either NIH or Seattle Criteria

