9.7.2.1 Missing or Incomplete Data and Loss to Follow-up

The eCRFs will be designed to minimize missing data and to optimize the integrity of collected data. Patients' records will not be excluded because of missing data but will be recorded for as missing if a specific covariate is not available for evaluation. The proportion of missing data will be reported for each measured variable in the study. Since data is collected from medical charts led as per standard of care, it is expected that data will be reasonably complete, however some missing data can also be expected.

A patient will be considered lost to follow-up if he or she is unable to be contacted by the study site for completion of questionnaire.

The following actions must be taken if a patient is unable to be contacted by the study site:

- The site must attempt to contact the patient as soon as possible and counsel the patient on the importance of completing the questionnaire and ascertain whether or not the patient wishes to and/or is able to continue in the study.
- In cases in which the patient is deemed lost to follow-up, the investigator or designee must make every effort to regain contact with the patient (where possible, 3 telephone calls and, if necessary, a certified letter to the patient's last known mailing address or local equivalent methods). These contact attempts are to be documented in the patient's medical record.
- If the patient continues to be unreachable, he/she will be considered to have withdrawn from the study with a primary reason of lost to follow-up.
- For patients who are lost to follow-up, the investigator can search publicly available records (where permitted) to ascertain survival status. This ensures that the data set(s) produced as an outcome of the study is/are as comprehensive as possible.

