9.7.2.2.3 Analysis of the Primary and Secondary Endpoints

Patient incidence proportions (and 95% Cls) for each of the specified outcome events will be summarized. KM estimates for time to first onset of each specified event will be provided.

For the events of interest, events that occur after a relapse or secondary malignancy will be censored as it is unlikely that events that occur after relapsed and treatment for relapse could be considered related to initial chemotherapy or blinatumomab treatment for the prior disease occurrence.

A comparison between the blinatumomab versus chemotherapy group will be conducted at the final follow-up in the study pending adequate sample size is enrolled $(\geq 50 \text{ patients per arm})$ and the blinatumomab and SOC groups are comparable (eg. there is overlap between PS distributions across the two groups, or no critical differences that cannot be accounted/adjusted for). Prior to comparison being conducted, covariates listed in Section 9.3.2 will be evaluated for differences between the two groups. Any covariates that are not comparable between the two (Wald chi-square or t-test, p-value < 0.25), will be evaluated as a covariate for adjustment in the models. The primary and secondary endpoint of discrete events (eg, incidence endpoints) will be compared by a logistic regression which will generate an odds ratio and 95% confidence interval of the odds of developing an event. Endpoints that are time-to-event will be compared by a Cox regression model which will generate hazard ratio and 95% confidence interval for the risk of developing an event. Also, we will additionally conduct a propensity score weighting analysis based on the covariates collected for this study. An additional sensitivity analysis may be done to adjust for the drop-in effect of patients receiving anti-cancer medications during follow-up.

A literature review of published data at the time of the final study report will be performed for the relevant endpoints. If there is any relevant scientific data publicly available by the time when the study ends (> 12 years later), Amgen will provide a comparative analysis. If a sufficient number of patients are identified in publicly available database with information on relevant confounding factors, Amgen will conduct a direct comparative analysis, but descriptive analyses will be undertaken either way.

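### Vaccination failure, named in the primary objective, has no denominator other than all eligible patients, including children never vaccinated after transplant or never checked for response

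*Protocol*

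**What the plan says.** Section 8.1 makes the primary objective the estimation of incidence in four impairment domains, and the immune domain expressly includes vaccine failure. Section 9.3.1 lists "Vaccination failure" as one of six immune items, beside leukopenia, low IgG, low IgM, low IgA and autoimmune disorders.

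On the analysis population, section 9.7.2 says "Tables will be presented for the total patient population (ie, those who meet the eligibility criteria". Section 9.7.2.2.3 says that patient incidence proportions with 95% intervals "for each of the specified outcome events will be summarized", and adds "KM estimates for time to first onset of each specified event will be provided". Neither section limits the denominator for any particular outcome.

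On missing data, section 9.7.2.1 says "Patients' records will not be excluded because of missing data" and that they will be "recorded for as missing if a specific covariate is not available for evaluation". It also promises the proportion missing for each measured variable. Section 9.7.2.2.1 mentions analysis sets without defining any.

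On ascertainment, sections 9.2.1 and 9.2.5 take data from charts of routine visits, and day 1 of follow-up is the date of alloHSCT. No vaccination and no response test is required. The covariate list in section 9.3.2 does not name vaccination, either at baseline or during follow-up.

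**The concern.** A vaccine cannot fail in a child who never received it, and a failure that nobody looked for will not be in the chart. A chart without such an entry looks the same whether the vaccine worked, was never given, or was given and never checked. With all eligible patients in the denominator, these three situations are pooled, and the proportion mixes the risk of failure with how often children were vaccinated and checked.

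This matters because section 7.2 gives the developing immune system, including vaccination with live vaccines, as a reason for the study. In a safety study, understating a named risk is the harmful direction. If vaccination or checking differs between the blinatumomab and chemotherapy groups, the crude comparison would also show a difference that is not one of risk.

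**Working it through.** **Plan's own figure.** Section 9.5 divides 52 long-term survivors per arm by a survival rate of 0.35: 52/0.35 = 148.6, rounded up to 149 per arm, 298 in total. This reproduces. It is used below only as the arm size N = 149; the protocol gives no evaluable share and no expected rate of vaccination failure.

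**Formula.** Let n be the evaluable patients (vaccinated after alloHSCT, response recorded), x the failures, p = x/n, and f = n/N. The proportion over all patients is x/N = p × f. It is therefore too low by the factor f, whatever p is.

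**Illustration.** Both f and p are assumptions: f runs from 25% to 90%, and p is about 20%. Counts are whole patients; intervals are Wilson 95%.

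| f | Among evaluable | Over all 149 |
|---|---|---|
| 90% | 27/134 = 20.1% (14.2 to 27.7) | 27/149 = 18.1% (12.8 to 25.1) |
| 75% | 22/112 = 19.6% (13.3 to 28.0) | 22/149 = 14.8% (10.0 to 21.3) |
| 50% | 15/74 = 20.3% (12.7 to 30.8) | 15/149 = 10.1% (6.2 to 15.9) |
| 25% | 7/37 = 18.9% (9.5 to 34.2) | 7/149 = 4.7% (2.3 to 9.4) |

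Check of the 50% row: f = 74/149 = 0.497, and 0.203 × 0.497 = 0.101. The all-patient interval is narrower as well as lower, and in this row it does not reach the 20.3% seen among evaluable patients.

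**Arm comparison.** Take f = 75% in one arm and 50% in the other, with p about 20% in both. Among evaluable patients the arms read 22/112 = 19.6% and 15/74 = 20.3%. Over all patients they read 22/149 = 14.8% and 15/149 = 10.1%, a gap of 7/149 = 4.7 points produced by the denominator.

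**Kaplan-Meier.** With time counted from alloHSCT, a never-vaccinated child stays in the risk set and adds event-free time until censored. KM handles shortened follow-up, but it does not remove patients who were never at risk.

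**Composite.** Vaccination failure changes the immune composite only in patients with none of the other five items. Section 9.5 expects some immune complication in all patients, and plans on 85% to 98% having at least one event. If that range held for the other five immune items alone (an assumption), only 100 − 98 = 2% to 100 − 85 = 15% of patients could have their composite status changed by vaccination failure.

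**The case against.** The strongest reply is that the sentence in section 9.7.2 names the population reported on, set against the treatment subgroups, and is not a rule for each component. Evaluable sets by component are commonly fixed in a statistical analysis plan, which is not among the documents, and the mention of analysis sets leaves room for them. Reporting missingness for each variable would show much of how many patients were assessed. This carries weight: the protocol does not forbid a better denominator. But the only population it states fits vaccination failure badly. Its missing-data coding rule speaks of covariates rather than outcomes, and a count of missing values discloses the problem without correcting the estimate.

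A reader might infer that the protocol counts unvaccinated or untested children as unaffected. No section says so; it is what follows if the stated population is applied literally.

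A reader might also extend the point to other components and replace their denominators too. The documents do not support that:

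- For the gonadal axis, a starting age would be an outside assumption and would drop disorders recorded earlier, and KM already censors death, exit and end of follow-up.
- For laboratory-defined items, testing in routine care is selective, so a tested-only denominator may overstate incidence.
- Executive-function questionnaires start at age 2 ("The preschool form (BRIEF-P) is available for ages 2-5"), but section 9.3.1 has the Vineland-3 capture cognition indirectly below that age, and surviving children soon reach it.

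Finally, the arm comparison is planned with covariate adjustment and propensity-score weighting as well. These may reduce a distortion that arises from baseline differences. Vaccination and checking after transplant are not among the listed covariates, so removal of the distortion cannot be assumed.

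**Conclusion.** The point holds for vaccination failure. Applied as written, the stated population understates this component by the factor f and can distort the crude arm comparison when f differs by arm. The direction rests on one assumption: that patients without a vaccination or a response check stay in the denominator without an event.

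The size is not known. Halving at f = 50% and the 4.7-point gap are illustrations, and the range in the table (20.1% reading as 18.1%, down to 18.9% reading as 4.7%) reflects assumed shares. Deriving a figure for this study from the age bands and the 35% survival in section 9.5 would go beyond the text: the protocol does not date that survival rate, its equal age groups refer to long-term survivors rather than enrolled patients, and it gives no timing or frequency of vaccination. The immune composite is affected less than the component.

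**What to change.** In sections 9.7.2 and 9.7.2.2.3, state that vaccination failure is reported among patients vaccinated after alloHSCT with a recorded response assessment, with time at risk counted from vaccination. Show the evaluable number by arm beside the estimate, and keep the total-population table alongside. Confirm that the eCRF captures the dates of vaccination and of the response check; this is best settled early, because dates not abstracted over years of follow-up may be hard to recover.

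For gonadal-axis and laboratory-defined components, only show the number assessed by arm beside the total-population and KM estimates. Do not replace their denominators or set an age threshold.

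This is a change of reporting and data capture only and asks for no vaccination or test. The cost is a few sentences and an eCRF check. The downsides are a smaller denominator, wider intervals (in the 50% row, 12.7 to 30.8 against 6.2 to 15.9) and possible selection among patients who were checked, which is why the total-population table stays.

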9.1 Study Design

This is a prospective, multi-country, multi-center observational study involving long-term follow-up of B-precursor ALL patients treated with either blinatumomab or SOC chemotherapy prior to alloHSCT. The study will have no effect on treatment practices of included patients due to its observational nature. The primary and secondary objectives relate to the description and comparison (pending adequate sample size is enrolled [≥ 50 patients per arm]) of the long-term safety profile of blinatumomab versus chemotherapy, prior to alloHSCT, in paediatric patients.

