9.5 Study Size

The targeted sample size for this study is approximately 298 patients. However, the actual number of patients that will be included in the study will depend on the results of site feasibility, willingness of patients (or their legal guardians/caregivers) or sites to participate in the study.

According to Marshall et al 2013, paediatric ALL patients are expected to have toxicity during intensification of therapy, generally related to hematological counts (Marshall et al, 2013). All patients also expect to have some immune complications after treatment end (Perkins et al, 2017) that will persist for some time.

Assuming that between 85%-98% of all patients will have at least one event, the expected ranges of sample sizes and relevant 95% CI is provided below. If 100 patients are enrolled.

95% C	onfidence	Interval o	of Estimated	Incidence o	of Adverse	Events by	Sample
-------	-----------	------------	--------------	-------------	------------	-----------	--------

S	ize	

Enrolled N Per Arm	Estimated Incidence of events	95% Confidence Interval*
150	98%	94.3%-99.3%
150	90%	84.1%-93.9%
150	85%	78.4%-89.8%
100	98%	93%-99.5%
100	90%	82.5%-94.5%
100	85%	76.7%-90.7%
75	98%	90.8%-99.3%
75	90%	82.0%-95.4%
75	85%	75.6%-91.6%
50	98%	89.5%-99.7%
50	90%	78.6%-95.7%
50	85%	71.5%-91.7%

* Wilson score interval

Sample size calculation for comparison analyses was calculated based on the number of long-term survivors needed. A risk difference of 10% (98% vs 88%) is considered as clinically significant. If the sample size is 52 long-term survivors per arm (104 in total), then a risk difference of as little as 10% will be detectable (p-value < 0.05).

Number of Long-term Survivors per Arm	Observed Risk Difference	P-value*
52/52	98% vs 88% = 10%	0.0455
40/40	98% vs 86% = 12%	0.0477
30/30	98% vs 83% = 15%	0.0477
20/20	98% vs 77% = 21%	0.0444

* z-test of two proportion comparison

Assuming a 35% long-term survival rate, the required number of patients entering the study per arm is 149 (52/0.35). Therefore, the number of patients entering the study needed to successfully fulfill the primary objectives while taking into account the 35% survival rate is 298.

Even though long-term survivors contribute the most essential data to this study, all enrolled patients contribute important information. If the total sample size is 149 patients per arm (298 in total), then a risk difference of as little as 5% will be detectable (p-value < 0.05).

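### The protocol calls 50 enrolled patients per arm an adequate size for the arm comparison, but Section 9.5 sizes that comparison at 149 enrolled (52 long-term survivors) per arm, and 50 misses Section 9.5's own criterion

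*Protocol*

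**What the plan says.** The condition for comparing the arms appears four times in the protocol: in the Abstract (Data Analysis), Section 9.1, Section 9.7.2 and Section 9.7.2.2.3. Section 9.7.2 has "Pending adequate sample size is enrolled (≥50 patients per arm), comparison analysis between blinatumomab and chemotherapy groups will be conducted". Section 9.1 has "pending adequate sample size is enrolled [≥ 50 patients per arm". Section 9.7.2.2.3 says the comparison is "conducted at the final follow-up in the study pending adequate sample size is enrolled", with the same figure of 50. The Abstract and Section 9.7.2.2.3 add that the groups must be comparable, for example with overlapping propensity scores.

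Section 9.5 sizes the comparison in another unit:

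- The basis: "Sample size calculation for comparison analyses was calculated based on the number of long-term survivors needed".
- The difference of interest: "A risk difference of 10% (98% vs 88%) is considered as clinically significant".
- The number: "If the sample size is 52 long-term survivors per arm (104 in total").
- What that number is meant to deliver: "a risk difference of as little as 10% will be detectable (p-value < 0.05").
- The enrolment that follows: "Assuming a 35% long-term survival rate, the required number of patients entering the study per arm is 149 (52/0.35"), or 298 in total.

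Section 9.5 adds that all enrolled patients contribute information, and it gives a separate detectability row for 149 enrolled per arm.

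**The concern.** One document gives two sizes for one comparison. The size it calls adequate (50 enrolled per arm) is about a third of the size it calls required (149 enrolled per arm), and nothing in the text explains the gap. The comparability condition concerns confounding and does not address size.

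Section 9.5 says actual enrolment will depend on site feasibility and on willingness to take part, so a shortfall against 298 is foreseen. In that case the floor decides whether the comparison goes ahead. The study is a category 1 safety commitment (Section 7.2). An odds or hazard ratio from a comparison that the protocol itself labels adequate could carry more weight than its numbers justify.

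**Working it through.** **Inputs.** All are from Section 9.5 unless noted: rates of 98% and 88%; criterion p < 0.05 from a two-proportion z-test on the observed difference; 52 survivors per arm; 35% long-term survival; 149 enrolled per arm. The floor of 50 enrolled per arm is from Sections 9.1, 9.7.2 and 9.7.2.2.3 and the Abstract. Section 9.5 does not state whether the test is one- or two-sided. The two-sided pooled version is the one that reproduces its table.

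**Formula.** z = d / √(2·p̄·(1−p̄)/n), where d is the observed difference and p̄ the mean of the two rates. For 98% vs 88%, p̄ = 0.93 and 2·p̄·(1−p̄) = 0.1302.

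**Reproducing the plan's figures.**

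| Survivors per arm | Observed rates | Stated p | Recomputed p |
|---|---|---|---|
| 52 | 98% vs 88% | 0.0455 | 0.0457 |
| 40 | 98% vs 86% | 0.0477 | 0.0479 |
| 30 | 98% vs 83% | 0.0477 | 0.0476 |
| 20 | 98% vs 77% | 0.0444 | 0.0446 |

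Enrolment: 52/0.35 = 148.6, rounded up to 149 per arm and 298 in total. The plan's figures hold on its own method.

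**At the floor, long-term survivors.** 50 × 0.35 = 17.5 per arm.

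- n = 17: z = 0.10/√(0.1302/17) = 1.143, p = 0.25.
- n = 18: z = 0.10/√(0.1302/18) = 1.176, p = 0.24.
- The smallest observed difference from 98% that reaches p < 0.05 is about 23 points (n = 17) or 22 points (n = 18). The last row of the plan's table, 20 per arm, already needs 21 points.

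**At the floor, all enrolled patients analysed.** n = 50 per arm.

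- 98% vs 88%: z = 0.10/√(0.1302/50) = 1.9597, p = 0.0500, just short of the 1.9600 needed.
- 98% vs 93% (5 points): p̄ = 0.955, z = 0.05/√(0.08595/50) = 1.206, p = 0.23. The 5-point row in Section 9.5 is for 149 per arm. Its stated p of 0.0375 is reproduced with 93% (0.0374), not with the printed 95% (0.159), so 93% is used here.

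**Power for a true 98% vs 88%.** Normal approximation: Φ[(0.10 − 1.96·√(0.1302/n)) / √(0.1252/n)], where 0.1252 = 0.98·0.02 + 0.88·0.12. The exact figure enumerates both binomials and counts the outcomes with |z| > 1.96.

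| Analysed per arm | Normal approximation | Exact |
|---|---|---|
| 17 | 20% | 10% |
| 18 | 21% | 12% |
| 50 | 50% | 51% |
| 52 | 52% | 53% |

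**Sensitivity to the 35%.** If long-term survival were 25% to 50%, the floor would leave 12.5 to 25 survivors per arm, with power of about 16% to 28% (normal approximation).

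**The case against.** The strongest reply is that Section 9.7 nowhere limits the comparison to long-term survivors. Section 9.7.2 tabulates the total eligible population. The logistic and Cox models use incidence and time to first event, to which patients who later die also contribute. On that basis 50 enrolled means about 50 analysed, and power of about 51% is close to the 53% at 52. This stands. A reader might infer that the comparison would run on about 17 patients per arm with almost no power. The documents support that only for a survivor-based comparison. That is how Section 9.5 sizes the study, but it is not how Section 9.7 defines the analysis set.

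Four other inferences are tempting and do not hold.

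- **That 50 is a survivor count misapplied to enrolled patients.** This is unproven. 50 is also the smallest row of the precision table in Section 9.5, whose column is enrolled patients per arm.
- **That a 50/248 split would satisfy the plan.** It would meet the total of 298 but not the 149 per arm that Section 9.5 states.
- **That a null result would be reported as no safety difference.** No passage says so. The primary objective is estimation, and the comparison yields a ratio with a 95% CI.
- **That the floor should simply become 52 survivors.** Section 9.5 has no power term, so 52 gives only about 53% power. The threshold would also depend on a post-treatment outcome for which no time point is given.

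The floor is also a minimum beside an unchanged target of 298. The weak case is permitted, not planned.

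**Conclusion.** The point holds as a contradiction between the stated floor and the protocol's own sizing. Four passages call 50 enrolled per arm adequate, while Section 9.5 requires 149. The floor fails Section 9.5's p < 0.05 criterion for the 10-point difference on either reading: clearly on long-term survivors, and by the narrowest margin with all enrolled patients analysed. The practical loss therefore depends on which patients carry the comparison.

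The figures assume equal arms, the rates of 98% and 88%, an unadjusted two-sided pooled z-test and, for the survivor counts, 35% survival. They do not describe the power of the adjusted logistic or Cox models.

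**What to change.** In the Abstract and Sections 9.1, 9.7.2 and 9.7.2.2.3, stop describing 50 enrolled per arm as adequate. Describe it as the minimum for reporting an adjusted estimate with its 95% CI. State that the 10-point detectability claim rests on the Section 9.5 size: 149 enrolled per arm, expected to give 52 long-term survivors.

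When either arm falls short of that size:

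- label the comparison descriptive;
- report the smallest difference that the achieved numbers could show, both for all enrolled patients and for long-term survivors;
- draw no conclusion of no difference from a non-significant result.

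The change is to wording only and needs no extra patients or data. Its cost is that, with low accrual, the comparison carries a weaker label.
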